### **3 INTRODUCTION**

This statistical analysis plan (SAP) for the final data analysis is based on the most recently approved clinical study protocol (CSP), electronic case report form (eCRF), and eCRF completion guidelines.

This is a Phase 2, randomized, double-blind, placebo- and TEZ/IVA-controlled, parallel group, multicenter study to evaluate the safety and efficacy of VX-121 in triple combination with TEZ/VX-561 and in triple combination with TEZ/IVA in subjects aged 18 years and older with cystic fibrosis.

This SAP (Methods) documents the planned final statistical analyses of efficacy endpoints and safety endpoints defined in the study protocol for VX18-121-101.

The Vertex Biometrics Department will perform the statistical analysis described in this document. SAS (Version 9.4 or higher) will be used to generate all statistical outputs (tables, figures, listings, and datasets).

The SAP (Methods) will be finalized and approved prior to the completion of Parts 1 and 2. Any revisions to the approved SAP will be documented and approved in an amendment to the SAP prior to the completion of Parts 1 and 2. Any changes made to the SAP Methods after the completion of Parts 1 and 2 will be documented in the clinical study report for this study.

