### **5.2 Secondary Endpoints**

- Absolute change from baseline in sweat chloride concentrations through Day 29
  - Absolute change from baseline in Cystic Fibrosis Questionnaire-Revised (CFQ-R) respiratory domain score at Day 29
  - PK parameters of VX-121, TEZ, VX-561, [REDACTED] and relevant metabolites
- [REDACTED]

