### Efficacy

The primary efficacy endpoint is the absolute change from baseline in ppFEV1 through Day 29. A sample size of 18 subjects per treatment group provides at least 90% power to detect a mean within-treatment change of 7 percentage points. These calculations assumed a standard deviation of 8 percentage points for the absolute change from baseline in ppFEV1 and were based on EAST, Version 6.4.1.

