##### **8.3.1.2 Primary Analysis for Parts 1, 2, [REDACTED]**

The null hypothesis to be tested is that the mean absolute within-group change from baseline in ppFEV1 through Day 29 is zero for VX-121 in triple combination (TC) with TEZ/VX-561 in Parts 1 and 2, [REDACTED] separately. A 2-sided *p*-value of 0.05 or less will be interpreted as sufficient evidence to reject the null hypothesis.

The primary analysis will be performed using a mixed-effects model for repeated measures (MMRM) with change from baseline in ppFEV1 at Day 15 and Day 29 as the dependent variable for each part, separately. The model will include treatment group, visit, and treatment-by-visit interaction as fixed effects and subject as a random effect, with the continuous baseline ppFEV1 as a covariate. For Part 1 the model will include 4 treatment groups: placebo, TC-5 mg, TC-10 mg, TC-20 mg. For Part 2, the model will include 2 treatment groups: placebo + TEZ/IVA, and TC-20 mg. [REDACTED]

[REDACTED] The model will be estimated using restricted maximum likelihood. Denominator degrees of freedom for the F test for fixed effects will be estimated using the Kenward-Roger approximation. An unstructured covariance structure will be used to model the within-subject errors. If the model estimation does not converge, a compound symmetry covariance structure will be used instead.

Conditional on the observed data and covariates, missing ppFEV1 data will be assumed to be missing at random; consequently, no imputation of missing data will be performed.

The adjusted means and 95% confidence intervals (CI) of the average treatment effect through Day 29 (average over Day 15 and Day 29 only) will be presented for all within-treatment and between-treatment comparisons, for each part. A 2-sided *p*-value will be provided for within-treatment comparisons.

Further, the adjusted mean and corresponding 95% CI for each treatment group and the treatment difference between each triple combination and placebo or TEZ/IVA at Day 15 and Day 29 will be provided, for each part. A 2-sided p-value will be provided for within-treatment comparisons.

The adjusted mean (with SE) obtained from the MMRM analysis at Day 15 and Day 29 will be plotted by treatment group, for each part.

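### Does adding a random subject effect to unstructured errors over two visits undermine the primary MMRM?

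*SAP*

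**What the plan says.** SAP 8.3.1.2 analyses change from baseline in ppFEV1 at Days 15 and 29, separately for each part, by REML with Kenward-Roger degrees of freedom. On the mean and subject terms it says: "The model will include treatment group, visit, and treatment-by-visit interaction as fixed effects and subject as a random effect". On the errors it says: "An unstructured covariance structure will be used to model the within-subject errors". On failure it says: "If the model estimation does not converge, a compound symmetry covariance structure will be used instead".

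The primary quantity is the average over the two visits. By-visit results are also reported: "the adjusted mean and corresponding 95% CI for each treatment group" at Days 15 and 29, and a figure: "The adjusted mean (with SE) obtained from the MMRM analysis at Day 15 and Day 29 will be plotted by treatment group".

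SAP 8.3.2.2 applies a similar model to sweat chloride and to the CFQ-R endpoint, which SAP 5.2 defines as "Absolute change from baseline in Cystic Fibrosis Questionnaire-Revised (CFQ-R) respiratory domain score at Day 29".

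Protocol 12.3.4.1 also lists subject as a random effect. It names compound symmetry as the only error structure, and PROC MIXED as the procedure. The notes to SAP Appendix A leave one value per subject in each visit window.

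**The concern.** A random subject effect adds the same variance to both visits and the same covariance between them. An unstructured 2 × 2 error matrix can already represent any variances and covariance, so the two components overlap. With one value per subject per visit, no replicates can separate them. The fallback sentence does not drop the random effect, so the overlap persists under compound symmetry. Neither document says that the subject phrase merely identifies the repeated-measures block.

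The overlap creates a flat direction in the likelihood, and some optimisers fail on such a direction. Failure is the SAP's trigger for compound symmetry, so a redundant phrase could in principle change the reported model. Compound symmetry forces equal variance at the two visits. If the true variances differ, the Day 15 and Day 29 SEs and confidence intervals would be misstated. CFQ-R, a Day 29 endpoint, would be exposed in the same way. SAP 8.3.1.4 plans no sensitivity analysis that would reveal a switch.

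**Working it through.** **1. The plan's own figure.** SAP 6.2 gives n = 18, a within-group change of 7, and at least 90% power. On the SD it says: "These calculations assumed a standard deviation of 8 percentage points for the absolute change from baseline". With two-sided alpha 0.05:

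- noncentrality = (7/8) × sqrt(18) = 3.712, with 17 degrees of freedom
- power = 93.8% from the noncentral t (96.0% from the normal approximation)

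The statement is reproduced. It does not involve the covariance parameterisation.

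**2. Counting parameters.** Let B be the variance of the subject effect and V the total covariance of the two visits.

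- Unstructured errors: V11 = B + R11, V12 = B + R12, V22 = B + R22. Four parameters, rank 3.
- Compound symmetry with common covariance C and residual variance E: V11 = V22 = B + C + E, V12 = B + C. Three parameters, rank 2.
- Without the subject effect, the ranks are 3 of 3 and 2 of 2.

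The literal model therefore has one redundant direction under either structure. V itself is identified in both.

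**3. Effect on estimates.** One Part 1 data set was simulated with groups of 9, 9, 18 and 18. The assumptions were an SD of 8 at each visit, covariance 45 and about 8% of Day 29 values missing. B was set to 0, 10, 20 and 30, with the error elements lowered to match:

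| Errors | REML objective | TC-20 mg average | SE |
|---|---|---|---|
| Unstructured, all four B | 464.2276 | 9.983 | 1.810 |
| Compound symmetry, all four B | 467.8357 | 9.929 | 1.804 |

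Within each row, all four settings of B gave the same values. In 200 data sets per part, the REML deviance with and without the subject effect (unstructured errors) differed by at most 1.7e-13.

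**4. Kenward-Roger.** V is linear in the parameters. If J maps the parameters to the identified elements of V and I is the information for those elements, the adjustment uses J (J' I J)⁻ J'. J has full row rank, so this equals the inverse of I for any generalised inverse. Adjusted SEs and degrees of freedom are therefore also unaffected, provided that the software handles the singular matrix.

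**5. Could it force a switch?** Own code, not SAS. An avoidable switch means that unstructured errors alone fit, the redundant model fails, and the fallback with the subject effect fits. Counts are per 300 simulated data sets, over visit SDs (Day 15/Day 29) of 8/8, 7/9 and 9/7:

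- ridge-stabilised Newton: 0 in every case
- unridged Newton, numerical derivatives: 1 to 2 (Part 1), 16 to 25 (Part 2)
- unridged Newton, analytic derivatives: no literal switch, because the fallback itself fitted in only 0 to 2 of 300

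The answer depends on the optimiser. The SAP's software statement is "SAS (Version 9.4 or higher) will be used to generate all statistical outputs", and SAS was not run.

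**6. What a switch would do.** With complete data, the variance of the two-visit average is proportional to (V11 + V22 + 2·V12)/4. Compound symmetry replaces each variance with their mean, so the sum, and hence the SE of the primary average, is unchanged. With 8% of Day 29 missing and correlation 0.7 (assumed), the SE ratio of compound symmetry to unstructured is 0.990 to 1.012; with 15% missing it is 0.980 to 1.024.

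For Day 29 alone, the complete-data ratio is sqrt((s15² + s29²)/2)/s29:

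- SDs 7/9: sqrt((49 + 81)/2)/9 = 8.062/9 = 0.896
- SDs 8/8: 1.000
- SDs 9/7: 8.062/7 = 1.152

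These Day 29 figures compare two error structures. They apply to any use of compound symmetry, with or without the subject effect, so they do not measure the redundancy.

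**The case for a change.** The strongest case for acting is that a plan should fix the model without relying on an unstated reading. The literal text lets two programmers code different models. Non-convergence has a prespecified consequence here, and by-visit estimates are deliverables. Under assumed SDs of 7/9 or 9/7, simulated coverage of the Day 29 95% interval under compound symmetry is about 92% or 97 to 98%. The remedy would be one sentence.

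The algebra stands, and so does the absence of a clarifying sentence. The step to harm does not. It needs the literal coding, an optimiser failure, a successful fallback that carries the same redundancy, and unequal variances at the two visits. The documents give one SD and no split by visit; at 8/8 the Day 29 effect is within about 1%. No CFQ-R SD is given, so no size can be stated there. Compound symmetry is also the structure in protocol 12.3.4.1, so a switch would lead to a model that the sponsor had already specified. Deleting the phrase would keep that fallback, so the Day 29 distortion would remain possible. Only the chance of an avoidable trigger could fall, and that chance has not been established for the planned software.

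**Conclusion.** Taken literally, SAP 8.3.1.2 and protocol 12.3.4.1 both over-specify the covariance by one direction. That is certain and rests on no assumed inputs. When the software absorbs the redundancy, the effect on adjusted means, SEs, Kenward-Roger quantities and stated power is nil. If it led to compound symmetry, the SE of the primary average would move by about 1%, and by at most 2.4% in the settings with 15% of Day 29 values missing. These sizes rest on assumed visit SDs, correlation and missingness, and convergence in SAS is untested.

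In a model called an MMRM with an explicit error structure, the natural reading of the subject phrase is that it identifies the repeated-measures block. An analyst who codes it that way gets the intended model, and one who codes it literally and converges gets the same answers. This is loose wording with no demonstrated gain from altering it, so the plan can stand.

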#### **8.3.1.4 Sensitivity Analysis**

No sensitivity analysis for the primary efficacy variable has been planned.

#### **8.3.1.5 Subgroup Analysis**

No subgroup analysis for the primary efficacy variable has been planned.

### **8.3.2 Analysis of Secondary Efficacy Variables**

#### **8.3.2.1 Definition of Variables**

Sweat chloride (SwCl): the SwCl value for a given visit will be calculated as the mean of the non-missing sweat chloride measurements obtained on the left and right arms at that visit. If one of the two arm measurements at a time point is missing, the other will be used as the mean. A volume  $\geq 15$   $\mu\text{L}$  is required for an accurate determination of sweat chloride. Any results reported as having volume  $< 15$   $\mu\text{L}$  will be considered missing. Any sweat chloride values reported as  $< 10$  mmol/L or  $> 160$  mmol/L will be considered missing.

Cystic Fibrosis Questionnaire-Revised (CFQ-R):

The CFQ-R is a validated CF-specific instrument that measures quality-of-life domains. This study uses CFQ-R for Adolescents and Adult (subjects 14 years and older). CFQ-R for Adolescents and Adult has a total of 50 questions to form 12 domains. Question 43, which is scored 1, 2, 3, 4, or 5, is not used in calculating any domains; all the other 49 questions are scored 1, 2, 3, or 4.

To calculate the score for each domain, the response scores on the negatively phrased questions are reversed (reversed scores = 5 – response scores) so that 1 always represents the worst condition and 4 always represents the best condition. In each domain, in cases where individual questions were skipped, the missing scores are imputed with the mean score of the non-missing questions for that domain.

The scaled score for each domain ranges from 0 (worst condition) to 100 (best condition). It is calculated as follows:

$$\text{Scaled score for a domain} = 100 \times (\text{mean}(\text{scores of all questions in that domain}) - 1)/3$$

The scaled score for a specific domain will not be calculated if more than half of the questions in the domain have missing scores.

Table 8-1 provides the questions included in each domain, the questions with the reversed scores, as well as the maximum number of missing questions allowed in order to be able to calculate a domain score.

**Table 8-1 CFQ-R for Adolescents and Adults (subjects 14 years and older)**

Domain	Questions		Questions with reversed scores	Maximum number of missing questions
	Total	Individual		
Physical	8	1, 2, 3, 4, 5, 13, 19, 20	13	4
Role	4	35, 36, 37, 38	35	2
Vitality	4	6, 9, 10, 11	6, 10	2
Emotion	5	7, 8, 12, 31, 33	-	2
Social	6	22, 23, 27, 28, 29, 30	23, 28, 30	3
Body	3	24, 25, 26	-	1
Eat	3	14, 21, 50	-	1
Treatment burden	3	15, 16, 17	15, 17	1
Health perceptions	3	18, 32, 34	18, 32, 34	1
Weight	1	39	-	0
Respiration*	6	40, 41, 42, 44, 45, 46	43	3
Digestion	3	47, 48, 49	-	1

\*: Question 43 not used to calculate any domain.

### 8.3.2.2 Analysis Method

#### 8.3.2.2.1 Absolute Change from baseline in Sweat Chloride through Day 29 (Parts 1, 2, [REDACTED])

[figure not shown]
The analysis of the absolute change from baseline in sweat chloride through Day 29 will be based on an MMRM similar to the primary analysis of the primary efficacy variable for Parts 1, 2, [REDACTED]. The presentation of results will also be similar.

#### 8.3.2.2.2 Absolute change from baseline in the CFQ-R respiratory domain score at Day 29 (Parts 1, 2, [REDACTED])

The absolute change from baseline in the CFQ-R respiratory domain score at Day 29 will be based on the *CFQ-R scaled scores*.

An MMRM similar to the primary analysis of the primary efficacy variable in Parts 1, 2 [REDACTED] will be used to analyze this variable. The presentation of results will also be similar.

## 8.4 Safety Analysis

For Parts 1 [REDACTED] all safety analyses will be based on data from the TE Period for all subjects in the Safety Set. For Part 2, all safety analyses will be based on the TE Period for the Treatment Period for all subjects in the corresponding Safety Set for Treatment Period, unless otherwise specified.

The overall safety profile of study drug will be assessed in terms of the following safety and tolerability endpoints:

- Treatment-emergent adverse events (TEAEs)
- Clinical laboratory values (i.e., hematology, serum chemistry, coagulation, and urinalysis)
- ECGs
- Vital signs including body weight and BMI
- Pulse oximetry
- Spirometry.

All safety data will be summarized by treatment group unless otherwise specified, for each part. Only descriptive analysis of safety will be performed and no statistical testing will be performed. The safety data during the Run-in Period will only be presented in listings, unless otherwise specified.

### 8.4.1 Adverse Events

For Parts 1 [REDACTED]

For analysis purposes, AEs will be classified as pretreatment AEs, TEAEs, or post-treatment AEs, defined as follows:

**Pretreatment AE:** any AE that started before the first dose date of study drug

**TEAE:** any AE that worsened (either in severity or seriousness) or that was newly developed at or after the first dose date of study drug through the end of the TE period.

**Post-treatment AE:** any AE that worsened (either in severity or seriousness) or that was newly developed after the TE period

For Part 2:

For analysis purposes, AEs will be classified as pretreatment AEs, TEAEs during the Run-in Period, TEAEs during the Treatment Period, and post-treatment AEs, defined as follows:

**Pretreatment AE:** any AE that started before the first dose date of study drug (TEZ/IVA) in the Run-in Period.

**TEAE during the Run-in Period:** any AE that worsened (either in severity or seriousness) or that was newly developed at or after the first dose date of study drug (TEZ/IVA) through the end of the TE period for the Run-in Period.

**TEAE during the Treatment Period:** any AE that worsened (either in severity or seriousness) or that was newly developed at or after the first dose date of study drug (TC or placebo+TEZ/IVA) through the end of the TE period for the Treatment Period.

**Post-treatment AE:** any AE that worsened (either in severity or seriousness) or that was newly developed after:

- the TE period for Run-in Period if the subject did not receive treatment in the Treatment Period, or
- the TE period for the Treatment Period if the subject received treatment in the Treatment Period.

For AEs with completely missing or partially missing start dates, if there is no clear evidence that the AEs started before or after study treatment for Parts 1 [REDACTED] or if there is no clear evidence that the AEs are pre-treatment or TEAE during the Run-in Period or post-treatment for Part 2, the AEs will be classified as TEAEs during the Treatment Period. Unless otherwise specified, TEAE refers to TEAE during the Treatment Period.

Details for imputing missing or partial start dates of adverse events are described in [Appendix D](#).

AE summary tables will be presented for TEAEs only, for the TE period for Parts 1 [REDACTED] and the TE period for Treatment Period in Part 2.

An overview of all TEAEs by treatment group and overall will be summarized in the following categories:

- Number of TEAEs (total number of TEAEs only);
- Subjects with any TEAEs;
- Subjects with TEAEs by strongest relationship;
- Subjects with TEAEs by maximum severity;
- Subjects with TEAEs leading to study drug discontinuation (discontinuation of any study drug);
- Subjects with TEAEs leading to study drug interruption (interruption of any study drug);
- Subjects with Grade 3/4 TEAEs;
- Subjects with related TEAEs;
- Subjects with serious TEAEs;
- Subjects with related serious TEAEs;
- Subjects with TEAE leading to death.

The following summary tables of TEAEs will be presented by treatment group:

- All TEAEs
- Grade 3/4 TEAEs
- TEAEs by strongest relationship
- TEAEs by maximum severity
- TEAEs leading to treatment discontinuation
- TEAEs leading to treatment interruption
- Related TEAEs
- Serious TEAEs
- Related serious TEAEs
- TEAEs leading to death

Summaries will be presented by MedDRA System Organ Class (SOC) and Preferred Term (PT) using frequency counts and percentages (i.e., number and percentage of subjects with an event). When summarizing the number and percentages of subjects, subjects with multiple occurrences of the same adverse event or a continuing adverse event will be counted once, and only the maximum severity level will be presented in the severity summaries, and the strongest relationship level in the relationship summaries.

Additional summary tables will be presented by treatment group and by PT for TEAEs showing number and percentage of subjects.

All AEs, including pre-treatment AEs, TEAEs for all applicable periods, and post-treatment AEs, will be presented in an individual subject data listing based on the All Subjects Set. In addition, separate listings containing individual subject adverse event data for TEAEs leading to treatment discontinuation, TEAEs leading to treatment interruption, Grade 3/4 TEAEs, SAEs and all deaths will be provided separately, with a flag indicating the TEAE status for SAEs and deaths.

In addition, the following tables for the Run-in period will be presented by overall based on the Safety Set for the Run-in period.

- An overview of TEAEs during the Run-in Period
- All TEAEs during the Run-in Period by SOC and PT

#### **8.4.2 Clinical Laboratory**

For the treatment-emergent laboratory assessments, the observed values and changes from baseline values of the continuous hematology, chemistry, and coagulation results will be summarized in SI units at each scheduled visit, by treatment group for each part.

The number and percentage of subjects meeting at least 1 threshold analysis criterion event, during the TE period for Parts 1 [REDACTED] or the TE period for Treatment Period for Part 2, will be summarized by treatment group for each part. The threshold analysis criterion shift from baseline will also be summarized for selected laboratory parameters. The threshold analysis criteria are provided in [Appendix E](#).

For selected LFT laboratory test (alanine aminotransferase [ALT], aspartate aminotransferase [AST], alkaline phosphatase [ALP], and total bilirubin), a scatter plot of the maximum treatment-emergent value versus the baseline value corresponding to  $\times$ ULN will be presented. Further, a scatter plot of the maximum treatment-emergent value of ALT and AST, separately, versus the maximum treatment-emergent value of total bilirubin corresponding to  $\times$ ULN will also be presented by treatment group, for each part.

Results of abnormal urinalysis and positive urine/serum pregnancy test will be listed in individual subject data listings only.

In addition, a listing containing individual subject hematology, chemistry, and coagulation values will be provided. This listing will include data from both scheduled and unscheduled visits.

#### **8.4.3 Electrocardiogram**

For the treatment-emergent ECG measurements, a summary of observed values and changes from baseline values will be provided at each scheduled visit and time point, by treatment group, for each part, for the following ECG interval measurements (in msec): RR interval, PR interval, QT interval, and QT corrected for HR (QTcF) interval, QRS duration, and Heart Rate (HR) (beats per minute).

The number and percentage of subjects meeting at least 1 threshold analysis criterion during the TE period for Parts 1 [REDACTED] or the TE period for the Treatment Period in Part 2, will be summarized by treatment group, for each part. The threshold analysis criteria are provided in [Appendix E](#).

In addition, a listing containing individual subject ECG values will be provided. This listing will include data from both scheduled and unscheduled visits.

